7.4.2. Visit 2: Day 1 – Randomization

The randomization visit will occur 14 ± 1 days after Visit 1 (Screening). This visit, the first visit of Stage 2, should be scheduled in the morning (if possible) to allow for administration of QID dosing of investigational product during the day for eligible subjects.

Eligible subjects who continue to meet the eligibility criteria (Section 8) will continue in the study. The site staff will perform/assess the following in the order suggested below:

- Subject-rated assessment of eye dryness
- Use of any concomitant medications since the last visit
- Occurrence of any AEs since the last visit and a status review of any ongoing AEs
- [REDACTED]

- Used and unused single-masked Stage 1 investigational product collected, counted, and compliance assessed [REDACTED]
- [REDACTED] assessment of bulbar conjunctival hyperemia
- [REDACTED]
- BCVA
- Slit Lamp Biomicroscopy
- Corneal fluorescein staining
- IOP measurement
- Upon verification of study eligibility, randomization of appropriate subjects to receive QID dosing of either KPI-121 0.25% ophthalmic suspension or vehicle.

The following will be performed for all randomized subjects:

- Instillation of randomized investigational product
- AE Assessment
- Dispensing of double-masked, investigational product (1 bottle) and instructions for administration

The first dose of double-masked investigational product will be administered in the clinic under the supervision of a designated dosing coordinator. This dosing coordinator, who is not responsible for study assessments, will also be required to dispense and retrieve investigational product to/from the subjects, provide instruction to the subjects regarding dosing of the investigational product, address study subjects' questions regarding the investigational product, [REDACTED]. Prior to administration of investigational product, subjects will be instructed regarding proper method for instillation of their assigned investigational product including but not limited to shaking investigational product bottle prior to each instillation. Since subjects will receive 1 dose of investigational product in the clinic, they will self-administer at most 3 additional doses of investigational product on the first day. Any Stage 1 doses taken on the morning of Visit 2 should be counted into the total 4 doses for the day.

- [REDACTED]

Instructions to subject:

- Dose investigational product as instructed

- Complete dosing information [REDACTED]
- Complete ocular discomfort assessments [REDACTED]
- Return for Visit 3 scheduled on Day 8 ± 1 day.

7.4.3. Visit 3: Day 8 ± 1 day – [REDACTED]

This visit will occur on Day 8 ± 1 day as calculated from Visit 2: Day 1, and the following evaluations will be performed:

- Subject-rated assessment of eye dryness
- Use of any concomitant medications since the last visit
- Occurrence of any AEs since the last visit and a status review of any ongoing AEs
- [REDACTED]

Instructions to subject:

- Dose investigational product as instructed
- [REDACTED]
- [REDACTED]
- Return for Visit 4 scheduled on Day 15 + 2 days.

7.4.4. Visit 4: Day 15 + 2 days – End of Study Visit

The end-of-investigational-product-use visit will occur on Day 15 +2 days as calculated from Visit 2: Day 1. The site staff will perform/assess the following in the order suggested below:

- Subject-rated assessment of eye dryness
- Use of any concomitant medications since the last visit
- Occurrence of any AEs since the last visit and a status review of any ongoing AEs
- [REDACTED]
- Used and unused double-masked investigational product collected, counted, and compliance assessed [REDACTED]
- [REDACTED] assessment of bulbar conjunctival hyperemia

- [REDACTED]
- BCVA
- Slit Lamp Biomicroscopy
- Corneal fluorescein staining
- IOP measurement
- Dilated ophthalmoscopy
- UPT for WOCBP
- Release of subject from the study

7.4.5. Unscheduled Visit

Any visits or procedures performed beyond those specified within the protocol must be documented in the Unscheduled Visit pages of the electronic case report form (eCRF). Unscheduled visits may include but are not limited to reporting adverse events (AEs), changes in concomitant medications, or ophthalmic assessments as deemed appropriate by an appropriately qualified physician. If the subject is discontinuing study participation at the unscheduled visit, the eCRFs for Visit 4 should be completed rather than the eCRFs for an Unscheduled Visit.

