12. ASSESSMENT OF SAFETY

12.1. Safety Parameters

An ophthalmic examination will be performed at all study visits, except at Visit 3, according to the schedule of events provided in Appendix 1. Safety parameters include:

- Assessments of AEs
- BCVA
- Slit lamp biomicroscopy
- Dilated ophthalmoscopy
- IOP measurement
- Pregnancy screen (performed only at Visits 1 and 4 on WOCBP)*

*All pregnancies are to be reported from the time informed consent is signed until Visit 4/End of study. Any report of pregnancy for any subject must be reported within 24 hours of site awareness to Kala or its delegate using the Pregnancy Report Form. The Pregnancy form should be faxed to [REDACTED] or emailed to [REDACTED]

Women who have a positive pregnancy test during the study will be withdrawn from the study treatment and, whenever possible, should complete all remaining study visits and assessments. Every effort should be made to gather information regarding the pregnancy outcome and condition of the infant. It is the responsibility of the investigator to obtain this information within 30 calendar days after the initial notification and approximately 30 calendar days postpartum.

Pregnancy complications such as spontaneous abortion/miscarriage, premature birth or congenital abnormality are considered SAEs. The SAE must be entered on the AE eCRF in EDC and the SAE fax cover letter completed then faxed to 1-[REDACTED] or emailed to [REDACTED]

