13.2. Analysis of Efficacy

13.2.1. Primary Efficacy Analyses

The primary analysis population will be the Intent-to-Treat (ITT) population, defined as all randomized subjects who received at least one dose of randomized investigational product. A subset of efficacy analyses will be examined for the Per Protocol (PP) population, the definition of which will be outlined in the Statistical Analysis Plan (SAP) and finalized prior to unmasking of study data pursuant to clinical data review. The specific details of endpoint testing will be elaborated in the SAP. If changes to the Statistical Analysis elaborated in the protocol are deemed necessary, those changes will be made prior to unmasking the study data and may only be elaborated in the Statistical Analysis Plan.

The trial will have 2 primary endpoints each tested at [REDACTED]:

1. Change in ODS scores in the ITT population [REDACTED]
[REDACTED]
2. Change in ODS scores in the ITT subgroup with more severe baseline ocular discomfort [REDACTED]
[REDACTED]
[REDACTED]
[REDACTED]
[REDACTED]
[REDACTED]
[REDACTED]
[REDACTED]

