13.2.2. Secondary Efficacy Analyses

Secondary efficacy endpoint comparisons will be performed between KPI-121 0.25% ophthalmic suspension group and the vehicle group [REDACTED] if the null hypotheses for the primary endpoints are rejected. The secondary endpoints testing will be [REDACTED]
[REDACTED]:

1. Change from baseline (Day 1) in bulbar conjunctival hyperemia scores in the ITT population at Visit 4 (Day 15 + 2 days)
[REDACTED] in the study eye [REDACTED]
[REDACTED].
2. Change from baseline (Day 1) in bulbar conjunctival hyperemia scores in the ITT population at Visit 4 (Day 15 + 2 days)
[REDACTED].
3. Change in ODS scores in the ITT population
[REDACTED]
[REDACTED].
4. Change from baseline (Day 1) in [REDACTED] corneal fluorescein staining scores in the ITT population at Visit 4 (Day 15 + 2 days) in the study eye.
5. Change in ODS scores in the ITT population
[REDACTED]
[REDACTED].

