13.6. Procedure for Accounting for Missing, Unused or Spurious Data

Any missing, unused, or spurious data will be noted in the final clinical study report. If more than 5% of data are missing, multiple imputation will be employed to analyze incomplete data sets under the assumption that missing data are, at worst, characterized as missing at random (MAR). Imputation will be carried out for the analysis of only the primary endpoints. The reasons for missing data will be recorded and the impact of these reasons and any treatment group imbalance on the assumption of MAR will be evaluated.

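### Does filing an early-exit exam on Visit 4 forms leave the hyperemia and staining secondaries undefined for subjects who leave before Day 15?

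*Combined protocol and SAP*

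**What the plan says.** **Endpoints.** Section 13.2.2 words secondaries 1 and 2 as "Change from baseline (Day 1) in bulbar conjunctival hyperemia scores in the ITT population at Visit 4 (Day 15 + 2 days"), and secondary 4 as the change in "corneal fluorescein staining scores in the ITT population at Visit 4 (Day 15 + 2 days) in the study eye". They are tested only "if the null hypotheses for the primary endpoints are rejected".

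**Population.** Section 13.2.1 takes ITT as the primary analysis population, "defined as all randomized subjects who received at least one dose of randomized investigational product". The same section adds: "The specific details of endpoint testing will be elaborated in the SAP".

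**Missing data.** Section 13.6 provides multiple imputation under MAR when more than 5% of data are missing, and then restricts it: "Imputation will be carried out for the analysis of only the primary endpoints". It also has missing data noted in the study report, and the reasons and any imbalance between groups weighed against the MAR assumption.

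**Schedule.** Section 12.1 says: "An ophthalmic examination will be performed at all study visits, except at Visit 3". Appendices 1, 4 and 8 place hyperemia and staining at Visits 1, 2 and 4 only.

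**Early exit.** Section 7.4.5 sends a discontinuation at an unscheduled visit to the Visit 4 forms ("the eCRFs for Visit 4 should be completed rather than the eCRFs for an Unscheduled Visit"). Section 7.4.6 deals with termination before Visit 4. It asks for all Visit 4 assessments if possible and otherwise a minimum list, which includes hyperemia but not corneal staining; it names no form. Section 8.3 has the reason for discontinuation recorded on the eCRF.

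**The concern.** With Day 1 (Visit 2) as baseline, hyperemia and staining each have one scheduled post-baseline exam, at Visit 4. Take a subject who leaves on Day 6. If the exit exam is used, the value is not from the Day 15 + 2 window. If it is set aside, there is no observed change score. The subject then drops out of the calculation, which seems to fall short of ITT, or has to be imputed, which section 13.6 does not provide for a secondary endpoint.

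Section 7.4.5 sharpens the worry. An early exam entered on Visit 4 pages could slip into an analysis dataset keyed on the visit label. Two analysts could then report different contrasts under the same ITT, Visit 4 heading. If exits were more common in one arm and exit exams were worse than completers' exams, the choice would move the estimated treatment difference and could be made with results in view.

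**Working it through.** **1. Is there a conflict in the text?** Set side by side for the Day 6 leaver:

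| Provision | What it governs | Consequence |
|---|---|---|
| 7.4.5 | Which form is completed at an unscheduled visit | Exam recorded on Visit 4 pages; nothing said about analysis |
| 7.4.6 | Exit before Visit 4 | Protocol treats the exit as preceding Visit 4; staining may not be examined |
| 7.4.4, 13.2.2 | Timing of Visit 4 and of the endpoint | Day 15 + 2 days; a Day 6 exam lies outside |
| 13.6 | Imputation | Primary endpoints only; a missing secondary is not imputed |
| 13.2.1 | ITT population | Who belongs to the set; no promise of an observed value for each member |

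Read together, these give one literal answer: observed values within the window, among ITT subjects. The actual study day and the recorded reason for discontinuation let the programmer identify an early exam whichever page it sits on. A likelihood model with baseline as a response could formally retain the leaver without imputation, but with no other post-baseline exam that subject adds almost nothing to the treatment contrast. The estimate is essentially the completers' one either way.

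**2. Can the plan's own figure be reproduced?** Section 13.4 gives power for ocular discomfort only (450 per group, above 99%; 225 per group, 95%), with effect size and per-test alpha blacked out. It cannot be reproduced, and it does not concern these secondaries.

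**3. How much could the choice matter?** All inputs except the 450 per arm are assumptions: two-sided 0.05, SD 1, and an effect giving 90% power with no exits.

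Power = Φ(d / √(1/n₁ + 1/n₂) − 1.96)

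d = (1.960 + 1.282) × √(2/450) = 0.2161 SD

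*Balanced exits, fraction f in each arm.* Left out: n = 450(1 − f). Kept at half effect: d(1 − f/2) with n = 450.

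| f | n per arm, left out | Power, left out | d, kept | Power, kept |
|---|---|---|---|---|
| 3% | 436.5 | 89.1% | 0.2129 | 89.1% |
| 5% | 427.5 | 88.5% | 0.2107 | 88.5% |
| 10% | 405 | 86.8% | 0.2053 | 86.9% |

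The two readings agree to about 0.1 point.

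*Unbalanced exits, 3% in one arm and 6% in the other, exit exams 0.5 to 1 SD worse than same-arm completers.* The readings differ by (6% − 3%) × shortfall:

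- 0.03 × 0.5 = 0.015 SD, or 0.015/0.2161 = 7% of the effect.
- 0.03 × 1 = 0.03 SD, or 14% of the effect.

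Left out (n = 436.5 and 423), power is 88.6%. Kept, the apparent effect is 0.2161 plus or minus the shift. Mixing shifted exits into an arm also raises its variance to 1 + f(1 − f) × shortfall². At a 1 SD shortfall that is 1 + 0.03 × 0.97 = 1.0291 and 1 + 0.06 × 0.94 = 1.0564.

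| Shortfall | Arm losing more | Apparent d | Power, SD held at 1 | Power, variance raised |
|---|---|---|---|---|
| 0.5 SD | Vehicle | 0.2311 | 93.4% | 93.2% |
| 0.5 SD | Active | 0.2011 | 85.5% | 85.1% |
| 1 SD | Vehicle | 0.2461 | 95.8% | 95.1% |
| 1 SD | Active | 0.1861 | 79.7% | 78.0% |

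The figures above 88.6% are not a gain in sensitivity. They show a shift produced by who leaves.

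**The case for a change.** The best case for acting is that section 13.6 is a positive restriction on imputation, not a silence awaiting detail, and that no readable passage says an out-of-window exam on a Visit 4 page is excluded. A dataset built on the visit label would include it by default. The section 7.4.6 minimum list adds an asymmetry: if exit exams were used, the hyperemia endpoints could include subjects that the staining endpoint lacks, all under one ITT label. A sentence in the SAP before unmasking would close this at almost no cost.

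Much of that stands as description. The window rule is not written in the text available, and the asymmetry is real. It does not make the plan wrong. The endpoint carries its own window, section 13.2.1 sends endpoint detail to the SAP, no SAP section appears in the text available, and section 13.2.2 is partly blacked out. The gap may already be filled there. The asymmetry arises only if exit exams are used, which the endpoint's wording does not support. A named sensitivity analysis for secondaries that are tested only after the primaries succeed is a matter of preference.

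The number of subjects involved should also be small. Randomized treatment lasts about 14 days. Rescued subjects are to stay through Visit 4 (section 9.2), and women with a positive pregnancy test are to complete remaining visits where possible (section 12.1). Only true study exits are affected.

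**Conclusion.** No change is called for. Followed as written, the plan gives an observed-in-window analysis of secondaries 1, 2 and 4, which is the literal reading of the endpoint and the one an experienced analyst would apply. The Visit 4 form instruction in section 7.4.5 is data capture and does not redefine the endpoint. The ITT label is not contradicted by a member without a value.

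On the assumptions shown, the choice of reading is worth about 0.1 point of power with balanced exits of up to 10%. It reaches 0.015 to 0.03 SD only if one arm loses twice as many subjects as the other and exit exams are 0.5 to 1 SD worse; neither is supported by anything in the documents. Confidence is moderate, because the SAP text is not available and parts of section 13.2.2 are blacked out. If the SAP turned out to analyse early exams as Day 15 values, the question would reopen.

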7.4.6. Early Termination Visit

In the event of termination prior to Visit 4, every attempt will be made to ensure that **all Visit 4 assessments are performed**. If this is not feasible, at least the following should be performed/assessed:

- Subject-rated assessment of eye dryness
- Use of any concomitant medications since the last visit
- Occurrence of any AEs since the last visit and a status review of any ongoing AEs
- Used and unused investigational product collected and compliance assessed [REDACTED]
[REDACTED].
- Bulbar conjunctival hyperemia [REDACTED]
- BCVA
- Slit lamp biomicroscopy

- IOP measurement
- UPT for WOCBP

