APPENDIX 8: CORNEAL FLUORESCEIN STAINING

Corneal staining will be performed at Visit 1, 2, and 4. Corneal staining assessment will be performed for both eyes using methods developed by the NEI Dry Eye Workshop^{5,6} with separate strips used for each eye.

Evaluation Technique

[figure not shown]
[figure not shown]
1. Use a Wratten #12 barrier filter in the assessment of fluorescein staining to enhance the appearance of the fluorescein.
2. Use sufficient unpreserved saline solution (study stock) to wet the entire area of fluorescein impregnation on a 1.0 mg strip. If the strip becomes too saturated, please discard and begin again with a new strip.
3. Within 15 seconds of wetting the strip, taking care not to touch the strip to the eye, instill the fluorescein sodium on the inferior palpebral conjunctiva.
4. Instruct the subject to blink several times to distribute the fluorescein staining.
5. Examine the cornea 2 minutes after instillation of fluorescein
6. Use a cobalt blue illumination (465 nm to 490 nm) and a 3-mm-wide scanning beam in each eye.
7. Compare corneal fluorescein staining in each eye with the standard by scoring each of the 5 corneal sections as described below:

Scoring system

1. Grade each of 5 sections of cornea (superior, inferior, nasal, temporal, central)
2. Provide grades for each of the 5 sections:
 - a. Grade by NEI scale (definition below) as 0, 1 (mild), 2 (moderate), 3 (severe)
3. Total score is obtained by summing each of the 5 sections of the cornea
 - a. NEI score will be from 0-15
4. Definitions
 - a. NEI Scoring System (0, 1, 2, 3)
 - i. Grade 0
No visible staining within the section of cornea being evaluated
 - ii. Grade 1 MILD
Small amount of micropunctate staining within the section of cornea being evaluated
 - iii. Grade 2 MODERATE
Medium amount of micropunctate staining within the section of cornea being evaluated or mild amount of macropunctate stain

iv. Grade 3 SEVERE

Significant amount of micropunctate or macropunctate staining within the section of cornea being evaluated

Grade 0

Grade 2

Grade 1

Grade 3

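### Minor, cheap to fix: the minimum early-termination list in 7.4.6 omits corneal fluorescein staining, a gated secondary endpoint read after baseline only at Visit 4 and not imputed

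*Combined protocol and SAP*

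**What the plan says.** **Early termination (7.4.6).** The first aim is a complete visit: "every attempt will be made to ensure that all Visit 4 assessments are performed". The fallback follows: "If this is not feasible, at least the following should be performed/assessed". The list then names eye dryness, concomitant medications, AEs, product return and compliance, bulbar conjunctival hyperemia, BCVA, slit lamp, IOP and a pregnancy test for women of childbearing potential. Staining and dilated ophthalmoscopy are not on it.

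**Visit 4 (7.4.4).** "Corneal fluorescein staining" is a separate item, placed after the slit lamp exam and before IOP.

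**Endpoint (13.2.2).** Secondary endpoint 4 is the change from Day 1 in "corneal fluorescein staining scores in the ITT population at Visit 4 (Day 15 + 2 days) in the study eye". Secondary endpoints are tested only if the primary null hypotheses are rejected.

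**Schedule (Appendix 8).** "Corneal staining will be performed at Visit 1, 2, and 4". Section 12.1 excludes Visit 3 from the ophthalmic examinations.

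**Missing data (13.6).** "Imputation will be carried out for the analysis of only the primary endpoints".

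**Safety (12.1).** "Dilated ophthalmoscopy" is listed as a safety parameter.

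**The concern.** The floor in 7.4.6 does not follow the endpoint list. It protects hyperemia, which supports secondary endpoints 1 and 2, and the slit lamp exam. It does not protect staining, which supports secondary endpoint 4, and the protocol gives no reason for the difference.

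A site can comply fully with 7.4.6, have the subject at the slit lamp, and still send the subject home without a post-baseline staining score. That subject remains in the ITT population, defined in 13.2.1 as all randomized subjects who took at least one dose, and is not replaced (8.3). With no later reading and no imputation, the value cannot be recovered by any analysis rule written afterwards. If the reasons for leaving are related to ocular response, the comparison loses subjects non-randomly.

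**Working it through.** The protocol states no figure for staining power, dropout or early termination, so there is none to reproduce. The stated power in 13.4 concerns ocular discomfort severity (ODS), and its effect sizes and significance levels are redacted. The check is therefore a comparison of lists, followed by an illustration under stated assumptions.

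**1. Is staining really absent from the floor?** The redactions in the 7.4.6 list follow the compliance item and the hyperemia item; no separate bullet is blacked out. Staining is printed openly as its own bullet in 7.4.1, 7.4.2 and 7.4.4, so redaction is an unlikely explanation.

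**2. Could the retained slit lamp exam supply the score?** No. The Appendix 7 grading covers lashes, lids, meibomian glands, conjunctiva, cornea (infiltrates, endothelium, edema), anterior chamber, lens and sclera. It has no fluorescein item. The 0–15 score comes only from the Appendix 8 procedure.

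**3. Is there another post-baseline reading?** No. Appendix 1 and Appendix 8 give Visits 1, 2 and 4. Visit 2 (Day 1) is the baseline and Visit 3 has no eye exam.

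**4. Does the missing-data rule cover it?** No. Under 13.6, multiple imputation applies only to the primary endpoints.

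**5. How many subjects?** Affected = 900 × e × f, where e is the early-exit rate and f is the share of exits who attend a termination visit but do not complete the full Visit 4 set. Neither is given. With f = 1, the upper bound:

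| e (assumed) | 900 × e |
|---|---|
| 2% | 18 |
| 5% | 45 |
| 10% | 90 |

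The real count is lower. Subjects who never return have no reading under either list, and subjects who complete the full set lose nothing.

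**6. Power.** Assume a staining comparison with 80% power at 450 per arm (two-sided 0.05), with equal loss in both arms. The standardized signal is 1.96 + 0.84 = 2.80 and shrinks by √(n/450); power ≈ Φ(2.80 × √(n/450) − 1.96).

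| Loss | n per arm | Power |
|---|---|---|
| 2% | 441 | 79.2% |
| 5% | 428 | 78.0% |
| 10% | 405 | 75.7% |

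**7. Bias.** Assume 5% exit on vehicle and 2% on active, with exiters 2 points worse than completers on the 0–15 scale in both arms. Leaving them out lowers the vehicle mean by 0.05 × 2 = 0.10 and the active mean by 0.02 × 2 = 0.04. The vehicle-minus-active difference shrinks by 0.10 − 0.04 = 0.06 point, or 0.06/15 = 0.4% of the scale. In this example the bias runs against the drug. If the two exit rates are swapped, the same 0.06 runs in its favor.

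**The case against.** The strongest reply is that the protocol already deals with most of this. Section 7.4.6 asks for all Visit 4 assessments first, 8.3 repeats the request for discontinuing subjects, and 7.4.5 sends a subject discontinuing at an unscheduled visit to the Visit 4 eCRFs. The list is a floor, not a target. Under 9.2, rescued subjects stop study medication but stay through Visit 4, which closes one main route to response-related loss. All of that stands, and it is why the point is minor. It does not explain why the floor leaves out one endpoint exam while keeping another.

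A second reply is that endpoint 4 is defined at Visit 4 (Day 15 + 2 days), so an earlier reading may not count. This stands in part: no visible rule says whether it does, and 13.2.1 leaves endpoint-testing detail to the SAP. But hyperemia has the same timing problem and is kept, and a reading never taken cannot be used under any rule. The fix must therefore cover both collection and use.

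Three stronger readings are tempting, and the documents do not support them.

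- A reader might infer that the primary measure, ODS, is also lost at early exit. The visible Visit 4 list does not name ODS either, and how it is captured is largely redacted, so its absence from 7.4.6 shows nothing.
- A reader might see "Subject-rated assessment of eye dryness" on the list and infer that it displaced staining. Section 11 lists eye dryness as an efficacy assessment, and Appendix 2 makes it a single mark on a line, so there is no real trade-off.
- A reader might infer that omitting dilated ophthalmoscopy leaves the subjects at highest risk unexamined. Nothing shows that early exits carry that risk, and the floor keeps AEs, BCVA, slit lamp and IOP. What remains is an unexplained mismatch with 12.1.

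**Conclusion.** The point holds as a minor, inexpensive improvement. A subject who exits on the 7.4.6 minimum list has no post-baseline value for secondary endpoint 4, and nothing visible in the plan supplies one. This conclusion rests on comparing the lists and needs no assumption about dropout.

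The size is unknown. The counts of 18, 45 and 90 are upper bounds at assumed exit rates, and the power and bias figures also rest on assumed inputs. On those assumptions the power loss is about 1 to 4 percentage points and the shift about 0.06 point, in a direction set by which arm loses more subjects. The endpoint is fourth of five secondaries and is tested only after the primaries succeed. A reader might infer that the staining comparison is materially biased; the documents do not support that.

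**What to change.** 1. Add corneal fluorescein staining, both eyes and in the Visit 4 order, to the minimum list in 7.4.6.
2. State in 7.4.6 that the early-termination reading is recorded on the Visit 4 eCRF, as 7.4.5 already directs for subjects discontinuing at an unscheduled visit.
3. State in 13.2.2 or the SAP, before unmasking, whether an early-termination staining reading enters the Visit 4 analysis.
4. Separately, reconcile the absence of dilated ophthalmoscopy from the 7.4.6 list with its listing as a safety parameter in 12.1, and give the reason for whichever position is kept.

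The cost is a few lines of text and a few extra minutes at an early-exit visit. Appendix 8 reads the cornea 2 minutes after instillation, and sites already perform the procedure at other visits. The downside is a slightly longer minimum visit for a subject who wants to leave.
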